### 6.2.1 Dose Modifications

**Table 1: Dose Modifications for APR-246**

	APR-246	Azacitidine
Starting dose level	3.7g 4h infusion days 1-4 q28d cycle	36 mg/m  sc or iv, days 1-5 q28d cycle
-1 dose level reduction	3.3g 4h infusion days 1-4 q28d cycle	36 mg/m  sc or iv, days 1-5 q28d cycle
-2 dose level reduction	3.0g 4h infusion days 1-4 q28d cycle	36 mg/m  sc or iv, days 1-5 q28d cycle

APR-246 is partially eliminated via the kidney and moderate renal impairment, defined by a creatinine clearance, or estimated glomerular filtration rate value of >30 to <60 mL/min, can lead to increases in plasma levels of approximately 30%. Therefore, for patients with moderate renal impairment, the dose of APR-246 should be reduced by 33% from the current dose (Table 2).

**Table 2: APR-246 Dose Modification in the Setting of Moderate Renal Impairment**

APR-246 Dose	33% Reduced Dose	Loading Dose (over 45 min)	Maintenance Dose (over 3 hr and 15 min)
3.7 g	2.5 g	1.1 g	1.4 g
3.3 g	2.2 g	1.0 g	1.2 g
3.0 g	2.0 g	0.9 g	1.1 g
<3.0 g	Please consult with Medical Monitor		

Monitoring renal function by assessment of serum creatinine prior to infusion of APR-246 is recommended in all patients.

Patients requiring >2 dose reductions for APR-246 will be permanently discontinued from study drug. Patients who permanently discontinue APR-246 or azacitidine should have follow-up within 30 days after discontinuation of all study treatment or resolution of the AE to ≤ grade 1, whichever occurs first, that includes all study assessments appropriate to monitor the event.

Azacitidine dose modifications will be per the prescribing information and institutional guidelines. Patients may continue with APR-246 without azacitidine if ≥

2 dose modifications have been due to cytopenias. APR-246 study drug may resume at last dosage received.

Any changes in dose must be recorded on the Dosage Administration Record CRF.

**Table 3: APR-246-Recommended Dose Modifications and Criteria for Treatment Interruption and Re-Initiation for Hepatorenal Toxicities**

Hepatorenal Toxicities	
Worst toxicity (CTCAE 5 Grade)†	Dose Modifications for APR-246
Serum Creatinine	
Grade 1 (< 1.5 × ULN)	Maintain dose level
Grade 2 (> 1.5 to 3.0 × ULN)	Omit dose until resolved to ≤ Grade 1, then: If resolved in ≤ 7 days, then maintain dose level If resolved in > 7 days, then ↓ 1 dose level
Grade 3 (> 3.0 – 6.0 × ULN)	If resolved in ≤ 7 days, then ↓ 1 dose level If resolved in > 7 days, discontinue patient from APR-246
Grade 4 (> 6.0 × ULN)	Permanently discontinue patient from APR-246
Bilirubin‡	
Grade 1 (> ULN - 1.5 × ULN)	Maintain dose level with LFTs* monitored as per protocol
Grade 2 (> 1.5 - 3.0 × ULN) with ALT or AST ≤ 3.0 × ULN	Omit dose until resolved to ≤ Grade 1, then: If resolved in ≤ 7 days, then maintain dose level If resolved in > 7 days, then ↓ 1 dose level
Grade 3 (> 3.0 - 10.0 × ULN) with ALT or AST ≤ 3.0 × ULN	Omit dose until resolved to ≤ Grade 1, then: If resolved in ≤ 7 days, ↓ 1 dose level If resolved in > 7 days, discontinue patient from APR-246
Grade 4 (> 10.0 × ULN)	Permanently discontinue patient from APR-246
AST or ALT	
Grade 1 (> ULN - 3.0 × ULN if baseline was normal; 1.5 - 3.0 × baseline if baseline was abnormal)	Maintain dose level with LFTs* monitored per protocol
Grade 2 (> 3.0 - 5.0 × ULN if baseline was normal; >3.0 - 5.0 × baseline if baseline was abnormal) without total bilirubin elevation to > 2.0 × ULN	Omit dose until resolved to ≤ Grade 1, then If resolved in ≤ 7 days, then maintain dose level If resolved in > 7 days, then ↓ 1 dose level
Grade 3 (> 5.0 - 20.0 × ULN if baseline was normal; > 5.0 - 20.0 × baseline if baseline was abnormal) without total bilirubin elevation to > 2.0 × ULN	Omit dose until resolved to ≤ Grade 1, then If resolved in ≤ 7 days, then maintain dose level If resolved in > 7 days, then ↓ 1 dose level
Grade 4 (> 20.0 × ULN if baseline was normal; > 20.0 × baseline if baseline was abnormal) without bilirubin elevation to > 2.0 × ULN	Permanently discontinue patient from APR-246
*(LFTs include albumin, ALT, AST, total bilirubin (fractionated if total bilirubin > 2.0 × ULN), alkaline phosphatase.	
† Common Terminology Criteria for Adverse Events (CTCAE) version 5.	
‡ For patients with Gilbert's syndrome, these dose modifications apply to changes in direct bilirubin only.	
* LFTs include albumin, ALT, AST, total bilirubin (fractionated if total bilirubin > 2.0 × ULN), alkaline phosphatase.	

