### **Other toxicity**

All dose modifications, interruptions or discontinuations must be based on the worst preceding toxicity as graded by the NCI Clinical Toxicity Criteria (NCI-CTCAE version 5). Once a dose has been reduced during a treatment cycle, re-escalation will not be permitted during any subsequent cycle (with exception of CNS events). If the administration of APR-246 is interrupted for reasons other than toxicity, then treatment with APR-246 may be resumed at the same dose. The same provision applies if the patient experienced an unacceptable toxicity not specifically described in this section, provided that this toxicity resolved to ≤ CTCAE grade 1, unless otherwise specified.

Day 1 of next cycle treatment with APR-246 and azacitidine can be delayed for up to 4 weeks (28 days) to allow for count recovery at Investigator discretion pending discussion with the Sponsor and Medical Monitor. Non-hematologic grade 4 treatment related adverse events will lead to permanent discontinuation, irrespective of recovery time, unless otherwise specified.

Exceptions would include nausea/vomiting/diarrhea which can be controlled by medications and/or asymptomatic electrolyte imbalances which can be corrected. In addition, in most instances, patients that experience a prolonged treatment interruption because of an adverse event and/or a grade 3 adverse event will decrease the dose of study drug after their recovery (see tables in this section for dose adjustment guidelines).

If any other drug-related grade 3 or 4 toxicity that is not clearly related to azacitidine is observed, APR-246 dose must be reduced for the next and subsequent cycles.

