Grade 3	If resolved with medical therapy, continue same dose level If not resolved despite treatment interruption and maximal medical therapy, stop infusion and ↓ 1 dose level for subsequent dose
Grade 4	Permanently discontinue patient from APR-246.
Infusion Related Reaction	
Grade 1	Maintain dose level.
Grade 2	Maintain dose level; Symptomatic management (e.g., antihistamines, corticosteroids, narcotics, IV fluids)
Grade 3	If resolved in < 4 hours with treatment interruption and medical therapy (e.g., antihistamines, corticosteroids, narcotics, IV fluids), continue same dose level and rate. If not resolved in < 4 hours despite treatment interruption and maximal medical therapy, stop infusion and ↓ 1 dose level for subsequent dose
Grade 4	Permanently discontinue patient from APR-246.
Nausea/Vomiting/Diarrhea	
Grade 1	Maintain dose level
Grade 2	If resolved, then maintain dose level If not resolved despite maximal medical therapy, then ↓ 1 dose level
Grade 3	If resolved, then maintain dose level If not resolved despite maximal medical therapy, then ↓ 1 dose level
Grade 4	Permanently discontinue patient from APR-246
Any Other Toxicity	
Grade 3 or 4	Delay dose until resolution to ≤ Grade 1, then ↓ 1 dose level

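### Table 3 has no row for bilirubin above 2 to 10 × ULN with both ALT and AST above 3 × ULN, and the provisions that then apply conflict and are sometimes less strict

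*Combined protocol and SAP*

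**What the plan says.** **Table 3, bilirubin block.** The Grade 2 row is headed "Grade 2 (> 1.5 - 3.0 × ULN) with ALT or AST ≤ 3.0 × ULN" and the Grade 3 row "Grade 3 (> 3.0 - 10.0 × ULN) with ALT or AST ≤ 3.0 × ULN". Both rows withhold the dose until recovery. Grade 2 then resumes at the same level if recovery takes up to 7 days, and one level down if longer. Grade 3 resumes one level down if recovery takes up to 7 days; otherwise "If resolved in > 7 days, discontinue patient from APR-246". The Grade 1 and Grade 4 rows carry no transaminase condition.

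**Table 3, AST/ALT block.** The Grade 2 and 3 rows apply "without total bilirubin elevation to > 2.0 × ULN". Both withhold, then resume at the same level (up to 7 days) or one level down (longer). The Grade 4 row, permanent discontinuation, applies "without bilirubin elevation to > 2.0 × ULN". The Grade 1 row is unconditional.

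**Table 5, Any Other Toxicity.** For Grade 3 or 4 only: "Delay dose until resolution to ≤ Grade 1, then ↓ 1 dose level". There is no time limit.

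**Section 6.2, Other toxicity.** Four statements bear on cases outside the rows:
- Same-dose resumption is allowed after an interruption not due to toxicity, and "The same provision applies if the patient experienced an unacceptable toxicity not specifically described in this section", once it has recovered to Grade 1 or less and unless otherwise specified.
- In most instances, a prolonged interruption for an adverse event, or a Grade 3 event, is followed by a lower dose.
- Any other drug-related Grade 3 or 4 toxicity not clearly due to azacitidine requires an APR-246 reduction.
- Treatment-related non-hematologic Grade 4 events lead to permanent discontinuation unless otherwise specified.

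**The concern.** Each block of Table 3 appears to be written for an isolated abnormality, with the other marker used to exclude patients from the row. No row receives the patients whom both blocks exclude. Those patients have both markers raised, and they pass to general provisions that were not written with the liver thresholds in mind.

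Two things are at stake. Sites that follow the text faithfully can stop, reduce or resume APR-246 in the same patient. In some combinations the literal result is also less strict than if only one marker were raised. The situation is foreseeable here: Section 5.2.1 admits patients with prior grade II-IV acute GVHD under conditions, and Appendix C stages liver GVHD by bilirubin.

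**Working it through.** The plan states no figure on this point, so there is none to reproduce. The check sets the row conditions against each other.

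**Step 1: coverage.** Take a normal baseline and cross four bilirubin bands (1.5-2, >2-3, >3-10, >10 × ULN) with three bands for ALT and AST together (>3-5, >5-20, >20 × ULN), which gives 4 × 3 = 12 combinations.
- Bilirubin 1.5-2: the AST/ALT rows apply (3 covered).
- Bilirubin >10: the unconditional Grade 4 bilirubin row applies (3 covered).
- Bilirubin >2-3 and >3-10: the bilirubin rows fail because both enzymes exceed 3.0 × ULN, and the AST/ALT rows fail because bilirubin exceeds 2.0 × ULN (2 × 3 = 6 uncovered).

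**Step 2: compare actions.** Split the 6 uncovered combinations by recovery within or beyond 7 days (12 cells). Actions are ordered: same dose < one level down (−1) < stop. All assume the dose is first withheld. T5 is Table 5; S6.2 is the Section 6.2 text.

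| Bilirubin | ALT and AST | Recovery | Bilirubin alone | AST/ALT alone | Both together |
|---|---|---|---|---|---|
| >2-3 | >3-5 | ≤7 d | same | same | same (S6.2) |
| >2-3 | >3-5 | >7 d | −1 | −1 | same, or −1 in most instances (both S6.2) |
| >2-3 | >5-20 | ≤7 d | same | same | −1 |
| >2-3 | >5-20 | >7 d | −1 | −1 | −1 |
| >2-3 | >20 | ≤7 d | same | stop | −1 (T5) or stop (S6.2) |
| >2-3 | >20 | >7 d | −1 | stop | −1 (T5) or stop (S6.2) |
| >3-10 | >3-5 | ≤7 d | −1 | same | −1 |
| >3-10 | >3-5 | >7 d | stop | −1 | −1 |
| >3-10 | >5-20 | ≤7 d | −1 | same | −1 |
| >3-10 | >5-20 | >7 d | stop | −1 | −1 |
| >3-10 | >20 | ≤7 d | −1 | stop | −1 (T5) or stop (S6.2) |
| >3-10 | >20 | >7 d | stop | stop | −1 (T5) or stop (S6.2) |

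**Step 3: count**, taking the same-dose provision in the second line.
- If Table 5 governs Grade 4: less strict than at least one single row in 7 of 12, and than both in 2 of 12.
- If the Section 6.2 Grade 4 sentence governs: 3 of 12 and 1 of 12.
- If the prolonged-interruption sentence replaces same-dose resumption in the second line, each count falls by one: 7 − 1 = 6 and 2 − 1 = 1, or 3 − 1 = 2 and 1 − 1 = 0.

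**Step 4: the three patterns behind the 7 cells** (2 + 1 + 4).
1. Grade 3 bilirubin beyond 7 days with Grade 2-3 AST/ALT (2 cells): discontinuation if bilirubin alone is raised, one level down without a time limit under Table 5. This holds under every reading above.
2. Bilirubin >2-3 × ULN with Grade 2 AST/ALT beyond 7 days (1 cell): each alone is reduced. Together, Table 5 does not apply because it starts at Grade 3, and Section 6.2 points both to the same dose and, usually, to a reduction.
3. Grade 4 AST/ALT with bilirubin >2-10 × ULN (4 cells): excluded from its own discontinuation row. Table 5 gives one level down; Section 6.2 gives permanent discontinuation if related.

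**Abnormal baseline.** AST/ALT grades then follow baseline while the bilirubin conditions stay on ULN. Section 5.2.1 admits ALT/AST below 2.5 × ULN. Suppose ALT and AST rise from 2 to 5 × ULN (5 / 2 = 2.5 × baseline, Grade 1) with bilirubin 5 × ULN. The Grade 3 bilirubin row is excluded, and the only bilirubin or AST/ALT row met is AST/ALT Grade 1, which keeps the dose level.

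**The case against.** The strongest reply is that Section 6.2 already deals with these patients. It bases modifications on the worst preceding toxicity, requires a reduction for other drug-related Grade 3 or 4 events, stops treatment for related non-hematologic Grade 4 events, and usually lowers the dose after a prolonged interruption. Whether raised bilirubin and transaminases, which have their own blocks, count as toxicity not described is open to interpretation. Tables 3 and 5 are titled as recommendations, and Sections 4.5 and 5.3 let the investigator stop for unacceptable toxicity, so no site is compelled to re-treat.

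Much of this limits the size of the point. It does not close the gap. The worst-toxicity principle says which grade to use; it does not remove the condition that excludes that grade's row. The prolonged-interruption sentence holds only in most instances and refers back to the same tables. The Grade 4 sentence yields to anything otherwise specified, and Table 5 specifies a different action for Grade 4. Section 6.2 also introduces its content as protocol rules for dose modification. Investigator discretion is a backstop, but it does not tell sites which provision applies.

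A reader might also infer that the count in the first-6 safety evaluation (Section 4.2) depends on the default chosen. The documents do not support that. The relevant criterion counts treatment-related non-hematological Grade 3-4 toxicity leading to dose modification or withdrawal. Pattern 2 is Grade 2 and does not enter it. In patterns 1 and 3 every candidate provision leads to a reduction or discontinuation, and either one counts.

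**Conclusion.** The gap is real and legible in the text: 6 of 12 combinations meet no bilirubin or AST/ALT row. The substitute provisions contradict each other for Grade 4 transaminases and for slow-resolving paired Grade 2 elevations. For slow-resolving Grade 3 bilirubin with Grade 2-3 transaminases, they are less strict than the isolated-bilirubin row. Because this governs when drug is stopped or resumed in liver injury, it should be corrected.

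Two broader readings are tempting and do not hold. Not every joint elevation is uncovered: bilirubin up to 2 × ULN, bilirubin above 10 × ULN and Grade 1 AST/ALT still meet a row. Nor is the combined case generally treated less strictly than either abnormality alone: that is so in at most 2 of 12 cells. In 5 of 12 (12 − 7) the result is equal to or stricter than both single rows under every reading considered.

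The result assumes a normal baseline, treatment-related toxicity, and a literal reading in which one enzyme at or below 3.0 × ULN satisfies the bilirubin rows, so that both must exceed it. The cell counts describe the rules and do not estimate how many patients would be affected.

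**What to change.** In the next amendment, reconcile Section 6.2 (Other toxicity), both liver blocks of Table 3 and the Any Other Toxicity entry of Table 5, so that concurrent bilirubin and AST/ALT elevation is explicitly covered by one rule. State which provision governs wherever Table 3, Table 5 and the Section 6.2 text differ, including for Grade 4 events. Say how the rule works when baseline transaminases are abnormal. The sponsor decides the clinical action; none is proposed here.

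The cost is a table row or footnote and a sentence on precedence. The metabolic panel is already scheduled, so no extra visits, samples or patients are needed.

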**Table 4: APR-246 Dose Modifications for Neutropenia with or without Fever**

Parameter †	Worst toxicity ‡	Dose modifications for APR-246	
Neutropenia with or without fever	Grade 3 or 4 neutropenic fever or worsening neutropenia from baseline to Grade 4 without fever	1 st occurrence	
 
Interrupt dosing and monitor patient; treat promptly.
 
Resume at current dose level if neutropenia and fever (if present) resolve to baseline within 7 days after onset.
 
If toxicity does not resolve to baseline despite maximal medical intervention(s) within 7 days of onset, then reduce APR-246 by 1 dose level once the toxicity resolves to baseline.
 
Initiate or reassess prophylaxis measures. Refer to Sections 6.3.3 and 6.3.4 for supportive management guidelines specific to infection prophylaxis and neutropenia, respectively.
 

		2 nd occurrence	
 
Hold all study treatments and monitor patient; treat promptly.
 
Assess current infection prophylaxis and adjust treatment plan as clinically indicated. Refer to Sections 6.3.3 and 6.3.4 for supportive management guidelines specific to infection prophylaxis and neutropenia, respectively.
 
While APR-246 and azacitidine are interrupted, consult with study medical monitor to determine if a dose modification of APR-246 is warranted.
 

Thrombocytopenia	Grade 4 (platelet count <25 x 10  /L) and major bleeding event	Permanently discontinue patient from APR-246.	

† Only applicable for patients with normal baseline absolute neutrophil count (ANC) and platelets

‡ Common Terminology Criteria for Adverse Events (CTCAE) version 5.

**Table 5: APR-246-Recommended Dose Modifications and Criteria for Treatment Interruption and Re-Initiation for Non-Hematological Toxicities**

Other Non-Hematological Toxicities	
Worst toxicity (CTCAE 5 Grade)†	Dose Modifications for APR-246
CNS - dizziness, dyskinesia and ataxia	
Grade 1	Maintain dose level
Grade 2	If resolved with medical therapy, continue same dose level If not resolved despite treatment interruption and maximal medical therapy, stop infusion and ↓ 1 dose level for subsequent dose
Grade 3	If resolved with medical therapy, continue same dose level If not resolved despite treatment interruption and maximal medical therapy, stop infusion and ↓ 1 dose level for subsequent dose
Grade 4	Permanently discontinue patient from APR-246.
Infusion Related Reaction	
Grade 1	Maintain dose level.
Grade 2	Maintain dose level; Symptomatic management (e.g., antihistamines, corticosteroids, narcotics, IV fluids)
Grade 3	If resolved in < 4 hours with treatment interruption and medical therapy (e.g., antihistamines, corticosteroids, narcotics, IV fluids), continue same dose level and rate. If not resolved in < 4 hours despite treatment interruption and maximal medical therapy, stop infusion and ↓ 1 dose level for subsequent dose
Grade 4	Permanently discontinue patient from APR-246.
Nausea/Vomiting/Diarrhea	
Grade 1	Maintain dose level
Grade 2	If resolved, then maintain dose level If not resolved despite maximal medical therapy, then ↓ 1 dose level
Grade 3	If resolved, then maintain dose level If not resolved despite maximal medical therapy, then ↓ 1 dose level
Grade 4	Permanently discontinue patient from APR-246
Any Other Toxicity	
Grade 3 or 4	Delay dose until resolution to ≤ Grade 1, then ↓ 1 dose level

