## 2.4 Azacitidine After Allogeneic HCT

Azacitidine (AZA) is a DNA methyltransferase inhibitor that shows significant clinical activity in both MDS and AML. Additionally, AZA has been shown to an effective salvage therapy in patients who relapse after HCT. Given the efficacy of AZA in these settings, maintenance strategies have been evaluated post-allogeneic transplant to prevent disease recurrence. The efficacy of low-dose AZA after allogeneic transplantation was originally reported in AML and subsequently in a larger phase I dose finding study including AML and MDS patients. In a cohort of forty-five patients who receive 4 cycles of post-HCT AZA, one year event-free survival and overall survival were reported as 58% and 77%, respectively, with reversible thrombocytopenia noted to be the dose-limiting toxicity. Tolerability and efficacy of AZA for one year after HCT has been reported by Craddox et al. Thirty seven patients were treated in AZA in the peri-transplant period with the day 100 and 1 year NRM was 0% and 8%, respectively, with no patients having any evidence of chronic graft versus host disease, underscoring the tolerability of the treatment. The 1-year and 2-year RFS were 57% and 49%, respectively, with patients demonstrating CD8+ T cell response demonstrating reduced relapse rate. Thus AZA dosing of 36 mg/m^2 subcutaneously for five consecutive days is effective and tolerable, and will be utilized at this dose for this study.

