### **6.3.4 Management of Neutropenia with or without Fever**

Monitor complete blood counts at the time of study enrollment and throughout the course of study treatment. Supportive measures such as antimicrobials for prophylaxis or in the setting of prolonged myelosuppression, and/or at the first signs of infection are recommended to reduce the risk of a serious or severe infection that may lead to a fatal outcome in the setting of neutropenia with or without fever (see Section 6.3.3).

Myeloid growth factors may be used in the setting of severe or prolonged neutropenia. Refer to Section 6.3 for a description of drugs that are not allowed to be used while a patient is on study treatment.

Refer to Section 6.2.1 for APR-246 dose modification in the setting of severe or life-threatening neutropenia with or without fever.

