#### **7.2.7 Cycles 2-4, Day 14**

- CMP
- Adverse events
- Concomitant medications

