#### **7.2.11 Cycles 5-12, Day 14**

- CMP
- Adverse events
- Concomitant medications

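### From Cycle 2 on, no blood count is scheduled between Day 1 and Day 28, so Table 4's afebrile Grade 4 trigger and 7-day recovery test rest on unscheduled counts with no stated timing

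*Combined protocol and SAP*

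**What the plan says.** Table 4 (Section 6.2.1) is triggered by "Grade 3 or 4 neutropenic fever or worsening neutropenia from baseline to Grade 4 without fever". At a first occurrence the site is told "Interrupt dosing and monitor patient; treat promptly". The dose level then depends on a 7-day clock that starts at onset: "Resume at current dose level if neutropenia and fever (if present) resolve to baseline within 7 days after onset", or "If toxicity does not resolve to baseline despite maximal medical intervention(s) within 7 days of onset, then reduce APR-246 by 1 dose level". A footnote limits the table to patients whose baseline ANC and platelets are normal. Section 6.2 (Other toxicity) adds that dose changes must rest on the worst toxicity that came before.

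The scheduled counts are these:

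- Cycle 1 (Sections 7.2.3 and 7.2.4): Days 7, 14, 21 and 28.
- Cycles 2-4 (Sections 7.2.5 to 7.2.8) and Cycles 5-12 (Sections 7.2.9 to 7.2.12): Day 28 and Day 1, with the Day 1 count waived if one was done in the previous 3 days.
- The visits headed "Cycles 2-4, Day 14" and "Cycles 5-12, Day 14" list a CMP, adverse events and concomitant medications, but no CBC. Table 11 agrees for Cycles 5-12.
- The synopsis (Criteria for evaluation) makes CBC and CMP weekly in the first month and monthly afterwards.

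Section 6.3.4 says "Monitor complete blood counts at the time of study enrollment and throughout the course of study treatment" but gives no frequency. Sections 7.0 and 7.2 allow unscheduled laboratory tests as needed.

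**The concern.** Afebrile Grade 4 neutropenia may give neither patient nor site a reason to ask for a count. If it begins and ends between Day 1 and Day 28 of a later cycle, no scheduled sample records it. If a Grade 4 value is found on Day 28, its onset lies somewhere in the preceding 27 days, so recovery within 7 days of onset cannot be judged from scheduled data.

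Two things are at stake. The first is consistent use of a stated dose rule, since its inputs would depend on each site's habits. The second is the safety endpoint. Section 3.4.1 makes the incidence and severity of laboratory abnormalities part of the second primary endpoint, and Section 9.1 tabulates them by maximum CTCAE grade. A maximum taken over fewer samples can only stay the same or fall. Cycle 1 is sampled about weekly and later cycles about monthly, so an apparent fall in hematologic toxicity over time could come from the schedule alone. Section 2.4 reports post-transplant azacitidine "with reversible thrombocytopenia noted to be the dose-limiting toxicity", so ascertainment of platelet counts matters too.

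**Working it through.** The plan states no figure on this point to reproduce. The check compares the gaps between scheduled counts with the 7-day window.

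**Inputs.** Count days come from Sections 7.2.3 to 7.2.12 and Table 11. For Cycle 1, the pre-dose count within 3 days of the first dose (Section 7.1.3) is taken as Day 1. For Cycles 2-4 the section text is used, because the copy of Table 10 available here has lost its column alignment.

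**Gaps.** Cycle 1: 6, 7, 7 and 7 days. Cycles 2-12: 28 - 1 = 27 days, or 24 to 30 with the 3-day window either side of Day 28, and up to 33 if the Day 1 count was taken 3 days early. The nominal gap is 27/7, or about 4 times the window.

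**Share missed.** Assume that onset is uniform over the cycle, that an episode lasts L days, and that no unscheduled counts are taken. The share missed by every scheduled count is the sum of max(0, gap - L) over the gaps, divided by the sum of the gaps. The base is 27 days (Day 1 to Day 28), or 28 days if the day from Day 28 to the next Day 1 is included.

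| Scheduled counts | Gaps (days) | Missed, L = 7 | Missed, L = 14 |
|---|---|---|---|
| Cycle 1 | 6, 7, 7, 7 | 0% | 0% |
| Cycles 2-12, 27-day base | 27 | 20/27 = 74% | 13/27 = 48% |
| Cycles 2-12, 28-day base | 27, 1 | 20/28 = 71% | 13/28 = 46% |
| With Day 14 added, 27-day base | 13, 14 | (6 + 7)/27 = 48% | 0% |
| With Day 14 added, 28-day base | 13, 14, 1 | (6 + 7)/28 = 46% | 0% |

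If the waiver merges the Day 28 and Day 1 counts into one, the gap is 28 days and the present schedule misses 21/28 = 75% and 14/28 = 50%.

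**What a Day 14 count does not settle.** The remaining gaps of 13 and 14 days still exceed 7 days. Such a count would show many more episodes, but it would not establish recovery within 7 days of onset.

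**The case against.** The monthly CBC looks deliberate: the synopsis, Sections 7.2.5 to 7.2.12 and Table 11 agree on it. Several provisions also soften its effect, and they rule out stronger readings.

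- A reader might infer that mid-cycle cytopenia goes unseen and that Table 4 cannot be applied. The documents do not support this. Unscheduled tests are allowed, Section 6.3.4 asks for counts throughout treatment, fever will usually prompt a count, and Table 4 requires monitoring once an event is known. What stands is that none of these clauses says when a count is due in a patient without symptoms.
- A reader might infer that patients are re-dosed during an unrecognised Grade 4 cytopenia. Every Day 1 has a count on that day or within 3 days before, and Section 6.2 allows the next cycle to be delayed up to 28 days for count recovery. A cytopenia still present would be visible. The one that can be missed has already recovered, although it may have lasted longer than 7 days.
- A reader might extend the 7-day point to platelets or to all patients. Table 4's platelet row requires Grade 4 with major bleeding and has no 7-day clock. The footnote excludes patients with abnormal baseline counts, while eligibility admits ANC from 500/µL and platelets from 20000/µL. Section 2.4 describes azacitidine without APR-246. The ascertainment point is not limited in this way.
- A reader might say that a typical nadir is never seen. The documents give no nadir timing, so no such figure can be stated.

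It is also fair that safety is summarised descriptively in a single arm with no test, that the formal safety evaluation follows Cycle 1, where counts are frequent, and that a patient's overall maximum grade still includes Cycle 1. This limits the consequence, but it does not make later cycles comparable with the first.

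**Conclusion.** The point holds in a limited form. After Cycle 1 the schedule contains no count between Day 1 and Day 28. Detection of afebrile Grade 4 neutropenia, and the 7-day test for patients with normal baseline counts, therefore depend on unscheduled counts that the protocol does not time. That sits poorly with the worst-toxicity rule in Section 6.2 and the monitoring instruction in Section 6.3.4. Maximum-grade hematologic results can be biased low in Cycles 2-12 and should not be compared directly with Cycle 1.

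The percentages are an illustration, not an estimate for this trial. They rest on uniform onset, fixed episode lengths and no unscheduled counts. Any extra counts that sites take would reduce the share missed, and nadir timing could move it either way. The schedule itself and the gap of about 27 days do not depend on these assumptions.

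**What to change.** For ascertainment of the safety endpoint, add a CBC with differential to the existing Day 14 draw in Sections 7.2.7 and 7.2.11 and in Tables 10 and 11. Align the synopsis, which now gives a monthly CMP while those sections also schedule one on Day 14.

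Separately, the sponsor must reconcile Table 4's 7-day criterion with the count schedule in the synopsis, Section 6.3.4, Sections 7.2.5 to 7.2.12 and Tables 10 and 11, because the Day 14 count alone does not resolve it. No dose rule or repeat-count rule is proposed here.

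The cost is at most 11 extra tubes per patient (one in each of Cycles 2-12), at a visit where Sections 7.2.7 and 7.2.11 already schedule chemistry. Slightly more cytopenia will be recorded.
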